12.3.3 Device Deficiencies

A device deficiency may or may not be associated with subject harm (ie, ADE or SADE); however, not all ADEs or SADEs are due to a device deficiency. The Investigator should determine the applicable category for the identified or suspect device deficiency and report any subject harm separately. Examples of device deficiencies include the following:

- Failure to meet product specifications (eg, incorrect IOL power)
- IOL defect
- Broken IOL optic
- Broken IOL haptic
- Scratched IOL optic
- Unsealed device packaging
- Suspect product contamination
- Lack of effectiveness

12.4 Monitoring for Adverse Events

At each visit, after the subject has had the opportunity to spontaneously mention any problems, the Investigator should inquire about AEs by asking the standard questions such as:

- “Have you had any health problems since your last study visit?”
- “Have there been any changes in the medicines you take since your last study visit?”

Changes in any protocol-specific ocular or systemic parameter evaluated during the study are to be reviewed by the Investigator. In addition, the subject’s responses to any questionnaire utilized during the study are to be reviewed by the Investigator. Any untoward (unfavorable and unintended) change in a protocol-specific parameter or questionnaire response that is clinically relevant, in the opinion of the Investigator, is to be reported as an AE. These clinically relevant changes will be reported regardless of causality.

12.5 Procedures for Recording and Reporting

AEs are collected from the time of informed consent. Any pre-existing medical conditions or signs/symptoms present in a subject prior to the start of the study (ie, before ICF is signed) are not considered AEs in the study and should be recorded in the Medical History section of the eCRF.

In addition, aqueous cells and flare, corneal edema, raised IOP and superficial punctate keratitis are examples of early post-operative findings that are typically observed following ocular surgery. These are not considered AEs if they can be reasonably expected to resolve within a week and not result in any untoward long term visual outcome impact.

For each recorded event, the ADEs and SAEs documentation must include: date of occurrence, severity, treatment (if applicable), outcome, and assessments of the seriousness and causality. In addition, the Investigator must document all device deficiencies reported or observed with test and control articles on the Device Deficiency eCRF. The site must submit all available information on ADEs, SAEs, and device deficiencies to the Study Sponsor immediately as follows:

- **ADEs or SAEs are documented on the *Adverse Device Effect and Serious Adverse Event* eCRF within 24 hours of the Investigator's or site's awareness.**
- **Device deficiencies are documented on the *Device Deficiency* eCRF within 24 hours of the Investigator's or site's awareness. Please include a printed copy of the completed *Device Deficiency* eCRF with product returns.**
- **Additional relevant information after initial reporting is to be entered into the eCRF as soon as the data become available.**
- **Document any changes to concomitant medications on the appropriate eCRFs.**
- **All relevant documentation such as Discharge Summary, Autopsy Report, Certificate of Death etc, should be faxed to the Study Sponsor at [name].**

NOTE: Should the EDC system become non-operational, the site must complete the appropriate paper *Adverse Device Effect and Serious Adverse Event Form* or *Device Deficiency Form*. The completed form is faxed to the Study Sponsor at [name] within 24 hours of the Investigator's or site's awareness; however, the reported information must be entered into the EDC system once it becomes operational.

Study Sponsor representatives and their contact information are provided in the Manual of Procedures that accompanies this protocol.

Further, depending upon the nature of the AE or device deficiency being reported, the Study Sponsor may request copies of applicable portions of the subject's medical records. The Investigator must also report all AEs and device deficiencies that could have led to a SADE according to the requirements of regulatory authorities or IEC/IRB.

12.5.1 Intensity and Causality Assessments

Where appropriate, the Investigator must assess the intensity (severity) of the AE as mild, moderate, or severe based on medical judgment with consideration of any subjective symptom(s), as defined below:

12.5.1.1 Intensity (Severity)

Mild An AE is mild if the subject is aware of but can easily tolerate the sign or symptom.

Moderate An AE is moderate if the sign or symptom results in discomfort significant enough to cause interference with the subject's usual activities.

Severe An AE is severe if the sign or symptom is incapacitating and results in the subject's inability to work or engage in their usual activities.

12.5.1.2 Causality

For every AE in the study, the Investigator must assess the causality (Related or Not Related to the medical device or test procedure). An assessment of causality will also be performed by a Study Sponsor physician utilizing the same definitions, as shown below:

Related An AE classified as related may be either definitely related or possibly related where a direct cause and effect relationship with the medical device or test procedure has not been demonstrated, but there is a reasonable possibility that the AE was caused by the medical device or test procedure.

Not Related An AE classified as not related may either be definitely unrelated or simply unlikely to be related (ie, there are other more likely causes for the AE).

12.6 Return Product Analysis

Study Sponsor representatives and their contact information are provided in the MOP that accompanies this protocol.

Alcon Products associated with device deficiencies and/or product related AEs should be returned and must include the Complaint # which will be provided by the Study Sponsor after the case is entered in the Study Sponsor's Global Product Complaint System (GPCMS).

12.7 Unmasking of the Study Treatment

Masked information on the identity of the assigned medical device should not be disclosed during the study. If the treatment code needs to be broken in the interest of subject safety, the Investigator is encouraged to contact an appropriate Study Sponsor representative prior to unmasking the information if there is sufficient time. Dependent upon the individual circumstances (ie, medical emergency), the code may be broken prior to contact with the Study Sponsor. The Study Sponsor must be informed in all cases in which the code was broken and of the circumstances involved. Additionally, the Study Sponsor may be required to unmask the information in order to fulfill expedited regulatory reporting requirements.

12.8 Follow-Up of Subjects with Adverse Events

The Investigator is responsible for adequate and safe medical care of subjects during the study and for ensuring that appropriate medical care and relevant follow-up procedures are maintained after the study.

The Investigator must provide the Study Sponsor with any new safety information (which includes new AEs and changes to previously reported AEs) that may affect the safety evaluation of the device. For AEs that are unresolved/ ongoing at time of subject exit from study, any additional information received at follow-up should be documented in the eCRFs up to study completion (ie, database lock).

Any additional data from these follow-up procedures performed up to 6 months after subject discontinuation or exit must be documented and available upon the Study Sponsor's request. All complaints received after this time period will be considered and processed as spontaneous (following the post-market vigilance procedures) and should be communicated to the medical device's manufacturer as per local requirements.

The Investigator should also report complaints on non-Alcon products directly to the manufacturer as per the manufacturer's instructions or local regulatory requirements.

12.9 Pregnancy in the Clinical Study

Pregnancy is not reportable as an AE; however, complications may be reportable and will be decided on a case-by-case basis. An Alcon form will be utilized to capture all pregnancy-related information until birth of the child.

13 ANALYSIS PLAN

The primary time point of interest is Month 3/Visit 4A except mesopic contrast sensitivity and spectacle use questionnaire. After all subjects complete Month 3/Visit 4A, the study database will be locked to conduct planned analyses. Results from these analyses will be used in a clinical study report for submission. The study will be continued until all subjects complete Month 6/Visit 5A (120-180 days post 2nd eye implantation), at which time the study database will be locked to report longer term safety and performance results.

13.1 Subject Evaluability

The final subject evaluability will be determined using the Deviations and Evaluability Plan (DEP) prior to breaking the code for masked treatment assignment and locking the database.

13.2 Analysis Data Sets

The primary analysis set for effectiveness analyses will be the all-implanted analysis set (AAS). AAS includes all randomized eyes with successful IOL implantation.

[REDACTED]

- [REDACTED]

- [REDACTED]

- [REDACTED]

The Safety Analysis Set will include all eyes with attempted IOL implantation (successful or aborted after contact with the eye).

13.3 Demographics and Baseline Characteristics

Summary statistics will be provided for demographic and baseline characteristics by IOL group. Number and percentage will be presented for categorical variables and descriptive statistics including mean, SD, minimum and maximum will be presented for continuous variables.

13.4 Effectiveness Analyses

A total of three hypothesis tests will be conducted to address the primary and secondary effectiveness objectives of the study. Overall Type I error will be maintained at the 0.05 level using a sequential testing approach.

13.4.1 Analysis of Primary Effectiveness Endpoint

The primary endpoint is monocular photopic DCIVA at 66 cm.

13.4.1.1 Statistical Hypotheses

The null and alternative hypotheses for the primary analysis are:

$$H_0: \mu_{\text{DFT015VA}} \geq \mu_{\text{SN60WFVA}}$$

$$H_A: \mu_{\text{DFT015VA}} < \mu_{\text{SN60WFVA}}$$

where μ_{DFT015VA} , μ_{SN60WFVA} , refer to the mean monocular photopic DCIVA at 66 cm for the test and control lenses, respectively, in the first implanted eye. [REDACTED]

13.4.1.2 Analysis Methods

For the primary effectiveness analysis, treatment group comparison for photopic DCIVA will be made and the primary objective will be demonstrated if (one-sided) $P < 0.025$ from a two-sample t-test.

Data poolability will be analyzed by testing a treatment by site interaction effect: first, the interaction effect between treatment and site will be tested using an alpha of 0.15; second, if the interaction effect is found significant, the final analysis model should include site as a random effect.

Descriptive statistics (mean, median, SD, number of eyes, minimum, maximum and [two-sided] 95% confidence interval) will also be provided for monocular photopic DCIVA, separately for each eye.

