11.1 Screening/Preoperative Visit (Visit 0)

Visit 0: -28-0 Days Prior to Visit 00, Bilateral Visit

Below is a list of study procedures to be done at Visit 0. It is recommended that procedures are performed in the order described below unless otherwise stated. All assessments must be documented in the source documentation and electronic case report form (eCRF), if applicable.

Data from the Investigator's previous routine clinical evaluation (eg, slit lamp exam) may be used, if the data 1) meet the requirements of this protocol and MOP, and 2) were collected within the -28 to 0 day preoperative time period.

1. Review study specific inclusion/exclusion criteria (eg, age, previous ocular history) to ensure that a potential subject meets all qualifications for participation in the study.

2. For a potential subject meeting all entry criteria via pre-screening, invite him/her to participate in the study, and carry out the informed consent process if he/she is interested. Refer to Section 11.9 Informed Consent Procedures.
3. Collect subject demographic, medical history information, and concomitant medication use.
4. Perform a urine pregnancy test, **IF** the subject is a woman of childbearing potential.

[REDACTED]

[REDACTED]

[REDACTED]

[REDACTED]

[REDACTED]

8. Measure and record [REDACTED] and BCDVA under photopic conditions at 4 m. [*Both Eyes, Bilateral*]

[REDACTED]

[REDACTED]

[REDACTED]

12. Record any AEs. Refer to Section 12 for further details.
13. Evaluate subject against all entry criteria. If subject fails criteria, screen fail the subject.
14. Document the target residual refractive error based on the IOL calculation power. [*Both Eyes, Bilateral*]
NOTE: This assessment may be done at any time after required biometry has been collected.
15. Identify the surgical eye for this study (determined by preoperative BCDVA).
16. Proceed with scheduling the surgery.

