13.11 Sample Size Justification

Effectiveness

The proposed sample size (N = 234; 130 Bilateral ACRYSOF IQ EDF IOL and 104 Bilateral ACRYSOF IQ Monofocal IOL) provides >99% power for the superiority hypothesis test on mean monocular DCIVA (66 cm) when tested at the 0.025 level of significance (one-sided) assuming the difference in means is -0.12 logMAR (SD = 0.18).

The proposed sample size (N = 234; 130 Bilateral ACRYSOF IQ EDF IOL and 104 Bilateral ACRYSOF IQ Monofocal IOL) provides 81% power for the non-inferiority

hypothesis with respect to mean monocular BCDVA (4 m) when tested at the 0.025 level of significance (one-sided) with a non-inferiority margin of 0.10 logMAR assuming the difference in means is 0.04 logMAR (SD = 0.16).

The proposed sample size (N = 234; 130 Bilateral ACRYSOF IQ EDF IOL and 104 Bilateral ACRYSOF IQ Monofocal IOL) provides >99% power for the superiority hypothesis test on mean monocular DCNVA (40 cm) when tested at the 0.025 level of significance (one-sided) assuming the difference in means is -0.12 logMAR (SD = 0.18).

The proposed sample size (N = 234; 130 Bilateral ACRYSOF IQ EDF IOL and 104 Bilateral ACRYSOF IQ Monofocal IOL) provides 74% power for the non-inferiority hypothesis with respect to mean monocular mesopic contrast sensitivity value when tested at the 0.025 level of significance (one-sided) with a non-inferiority margin of -0.15 log unit assuming the difference in mean is -0.02 log unit (SD = 0.38).

The expected sample size (N = 131) will provide 84% power, with $\alpha=0.025$, 1-sided, to detect a difference of 25% in proportion of subjects who respond “Never” to Q1 and Q3 of the spectacles use questionnaire respectively, assuming a 50% rate in the ACRYSOF IQ EDF IOL group.

Approximately 260 subjects will be randomized to achieve 234 subjects who complete the study. It is expected that approximately 131 subjects will respond to spectacle use questionnaire in this study.

Adverse Events

For any event where zero incidences is observed in 130 operative eyes with ACRYSOF IQ EDF IOL, the upper limit of the 95% 1-sided exact binomial confidence interval is less than 2.3%. Thus, with 95% confidence the true adverse event rate is less than 2.3%.

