4.3.2 Secondary Effectiveness Analyses

4.3.2.1 Best Corrected Distance Visual Acuity at 4 m

The statistical model associated with the hypotheses for the first secondary effectiveness analysis will be tested by generating a one-sided 97.5% upper confidence limit based on the difference (ACRYSOF IQ EDF IOL – ACRYSOF IQ Monofocal IOL) in means using a two-sample t-test at Month 3/Visit 4A. The upper bound of the one-sided 97.5% confidence limit will be compared to the margin, 0.10 logMAR. If the upper bound is less than the margin, the null hypothesis will be rejected and it will be concluded that ACRYSOF IQ EDF IOL is non-inferior to ACRYSOF IQ Monofocal IOL for best corrected distance visual acuity at 4 m. The SAS pseudo code is identical to that of the primary analysis.

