4.3.2.4 Mesopic Contrast Sensitivity With and Without Glare

The hypotheses for the fourth secondary effectiveness analysis will be tested by generating a one-sided 97.5% lower confidence limit based on the difference in means (ACRYSOF IQ EDF IOL – ACRYSOF IQ Monofocal IOL) using a two-sample t-test. The lower bound of the one-sided 97.5% confidence limit will be compared to the margin, -0.15 log unit. If the lower bound is greater than the margin, the null hypothesis will be rejected and it will be concluded that ACRYSOF IQ EDF IOL is non-inferior to ACRYSOF IQ Monofocal IOL for monocular mesopic contrast sensitivity. Monocular mesopic contrast sensitivity without glare at 12 cycles per degree will be tested followed by monocular mesopic contrast sensitivity with glare at 12 cycles per degree.

Scoring methods for log contrast sensitivity values are described in details in Section 5.3.3.

To assess the quantitative extent of bias resulting from subjects who cannot identify the sample patch, a censored regression model (which is a generalization of the standard Tobit model) ^[6, 7] will be used to estimate the difference in means and the corresponding interval of the log contrast sensitivity values while accounting for censored observations. The following SAS pseudo codes are shown, as an example, for mesopic contrast sensitivity without glare at 12 CPD measured in the 1st implanted eyes.

```
data mcsdata;
  set mcsdata;
  if      cpd12= -1 then logCS = 0.609999;
  else if cpd12=  0 then logCS = 0.61;
  else if cpd12=  1 then logCS = 0.91;
  else if cpd12=  2 then logCS = 1.08;
  else if cpd12=  3 then logCS = 1.25;
```

```

else if cpdl2= 4 then logCS = 1.40;
else if cpdl2= 5 then logCS = 1.54;
else if cpdl2= 6 then logCS = 1.69;
else if cpdl2= 7 then logCS = 1.84;
else if cpdl2= 8 then logCS = 1.99;

if lens='SN60WF' then IOL = 0;
else if lens = 'DFT015' then IOL = 1;
run;

proc qlim data=csdata(where=(lens='SN60WF' or lens='DFT015'));
  where glare = 'without Glare' and sureye = '1st';
  model logCS = IOL / censored(lb=0.609999);
  ods output ParameterEstimates = param2;
run;

```

4.3.2.5 Proportion of Subjects Who Respond "Never" to Q1 and Q3 of the Spectacle Use Questionnaire

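### Adjusting the BCDVA and contrast sensitivity non-inferiority tests for first-eye preoperative BCDVA and age could add power at very little risk; the planned t-tests are valid but leave this unused

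*Protocol*

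**What the plan says.** **The two tests.** For BCDVA, SAP 4.3.2.1 builds the upper limit on the difference "in means using a two-sample t-test at Month 3/Visit 4A" and reuses the primary analysis code, whose only model term is the lens. For mesopic contrast sensitivity at 12 cycles per degree, SAP 4.3.2.4 forms the lower limit "using a two-sample t-test. The lower bound of the one-sided 97.5% confidence limit will be compared to the margin, -0.15 log unit". The censored regression added there as a bias check also has lens as its only term. Protocol 13.4.2.2 gives the same methods.

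**What is collected.** Protocol 11.1 measures at Visit 0, in both eyes, "and BCDVA under photopic conditions at 4 m", the same distance and lighting as the first secondary endpoint. The worse eye on that measurement is operated on first (protocol 8.1), and the first eye supplies the confirmatory data. Demographics are recorded at the same visit.

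**How site and age are used.** For the primary DCIVA analysis, treatment by site is tested at 0.15, and "if the interaction effect is found significant, the final analysis model should include site as a random effect" (protocol 13.4.1.2). SAP 4.3.1 expands this into two mixed models compared by BIC. Age category and site are also descriptive subgroup factors for the visual acuity endpoints (SAP 4.5).

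**Sequence.** Under SAP 4.4, Month 6 testing starts only if the primary and both Month 3 secondary nulls are rejected, and testing stops at the first failure.

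**The concern.** BCDVA and contrast sensitivity are the two continuous endpoints with limited stated power; DCIVA and DCNVA are both above 99%. A missed BCDVA result would forfeit every Month 6 test, including contrast sensitivity and spectacle use. Contrast sensitivity is planned below 80%, and its with-glare test is reached only through the without-glare test.

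Any outcome variance that the baseline values could explain stays in the error term of these two tests. Conditional use of site is written only for an endpoint that has almost no power left to gain. The question is how much adjustment could return, and what it would cost if the baseline values turned out to carry no information.

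**Working it through.** **Inputs (protocol 13.11).** First eyes: 130 test and 104 control, N = 234. BCDVA: "when tested at the 0.025 level of significance (one-sided) with a non-inferiority margin of 0.10 logMAR", assumed difference 0.04, SD 0.16. Contrast sensitivity: "when tested at the 0.025 level of significance (one-sided) with a non-inferiority margin of -0.15 log unit", assumed difference -0.02, SD 0.38. The share of variance explained by the covariates, R², is not in the documents and is varied below as an assumption.

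**Step 1: reproduce the stated power.** SE = SD × √(1/130 + 1/104) = SD × 0.1316.

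- BCDVA: distance to margin 0.10 - 0.04 = 0.06; SE = 0.16 × 0.1316 = 0.02105; ratio 2.850. Normal power Φ(2.850 - 1.960) = 81.3%; noncentral t on 232 df, 81.0%.
- Contrast sensitivity: distance -0.02 - (-0.15) = 0.13; SE = 0.38 × 0.1316 = 0.0500; ratio 2.600. Normal power Φ(2.600 - 1.960) = 73.9%; noncentral t, 73.6%.
- DCIVA (difference 0.12 in size, SD 0.18): 99.9%. DCNVA has the same inputs.

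The protocol's 81% and 74% both reproduce. SAP section 7 gives 74% for BCDVA from the same inputs; those inputs give 81%, so the two documents need reconciling on that separate point.

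**Step 2: power after adjustment.** With k extra model terms, the variance of the adjusted lens difference is about

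SD² × (1 - R²) × (1/130 + 1/104) × [1 + k/(N - k - 3)], with 232 - k df.

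The factor (1 - R²) is the gain. The bracket is the price of chance imbalance in the covariates between arms.

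- Preoperative BCDVA and age, k = 2: bracket = 1 + 2/229 = 1.0087.
- Those two plus about 16 sites as fixed effects (15 contrasts), k = 17: bracket = 1 + 17/214 = 1.0794.

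Worked case for BCDVA, k = 2, R² = 0.10: SD = 0.16 × √0.90 × √1.0087 = 0.1525; SE = 0.0201; ratio 2.99; power 84.6% on 230 df.

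**Step 3: results (BCDVA / contrast sensitivity; unadjusted 81.0% / 73.6%).**

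| Assumed R² | Two covariates (k = 2) | Plus fixed sites (k = 17) |
|---|---|---|
| 0 | 80.7% / 73.2% | 78.0% / 70.3% |
| 0.05 | 82.6% / 75.3% | 80.0% / 72.5% |
| 0.10 | 84.6% / 77.6% | 82.1% / 74.7% |
| 0.20 | 88.5% / 82.2% | 86.3% / 79.6% |
| 0.30 | 92.2% / 86.9% | 90.4% / 84.6% |

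Each row uses the same R² in both columns. Sites that explain variance of their own would move the right-hand column to a lower row.

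**Step 4: break-even.** Adjustment pays when (1 - R²) × bracket is below 1. For k = 2 that needs R² above 1 - 1/1.0087, about 0.01. For k = 17 it needs R² above 1 - 1/1.0794, about 0.07. Contrast sensitivity reaches 80% power at R² of about 0.15.

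**The case against.** **The t-test is valid.** It is prespecified, it suits a randomized comparison, and it matches the power calculation. A reader might infer from the unused covariates that the planned analysis is wrong or biased. The documents do not support that. This objection stands in full and limits the point to efficiency.

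**The gain is not documented.** No correlation between baseline values and outcomes is given, and a strong one is not obvious. Preoperative BCDVA is measured with the cataract in place and the outcome after its removal. Protocol 9.2 also excludes retinal, optic nerve, glaucomatous and amblyopic eyes, which removes part of what could link the two. This stands as to the size of the gain. It does not remove the imbalance between a possible loss of 0.3 to 0.4 points and a possible gain of several.

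**Adjustment is not free.** A reader might infer that covariates and site can all be added at no cost. Counting lost degrees of freedom alone gives that impression: with k = 17 and R² = 0, BCDVA power stays at 81.0%. Once chance imbalance is counted it is 78.0%. Site-stratified allocation would shrink that cost, but the readable randomization text (protocol 10.2, SAP 1.3) does not state it. This objection rules out the fixed site effects.

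**Site is not ignored.** The primary analysis has a conditional route to a site model, site is a subgroup factor, and the shared pseudo-code for BCDVA and DCNVA might be read as carrying the site step over, although SAP 4.3.1 names primary outcomes. A claim that the plan disregards site would be too strong.

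**Redaction.** Parts of the analysis text are blacked out, so a supportive adjusted analysis cannot be excluded. The confirmatory tests themselves are readable and are unadjusted.

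**Conclusion.** The point holds as an efficiency recommendation for the two non-inferiority endpoints. With first-eye preoperative BCDVA and age in the model, an assumed R² of 0.10 to 0.20 adds about 4 to 8 points of power for BCDVA (81.0% to between 84.6% and 88.5%) and about 4 to 9 for contrast sensitivity (73.6% to between 77.6% and 82.2%). At R² = 0 the cost is 0.3 and 0.4 points.

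These figures rest on the protocol's means, SDs and 130/104 completers, a linear covariate effect, and an R² that the documents do not supply. DCIVA and DCNVA, already above 99%, have nothing material to gain. The conclusion does not extend to fixed site effects, which lower power unless the model's R² exceeds about 0.07.

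**What to change.** In protocol 13.4.2.2 and SAP 4.3.2.1 and 4.3.2.4, take the one-sided 97.5% confidence limit for BCDVA and for contrast sensitivity (without and with glare) from a prespecified ANCOVA with treatment, first-eye preoperative BCDVA and age. Margins, direction and testing order stay as they are. Keep the two-sample t-test as a sensitivity analysis. State that R² is an assumption and that the sample size does not rely on it.

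The same model may be used for DCIVA and DCNVA for consistency, without expecting a gain. Do not add about 16 fixed site effects.

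The cost is a change of wording in both documents and two terms in the model statement. No new data are needed, and the risk is at most about 0.3 to 0.4 points of power if the covariates explain nothing.
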